1 TRIAL SUMMARY

Table 1. Trial summary

Master protocol title	CoReCCT - Confederation of Respiratory Critical Care Trials
Domain protocol title	Neurally Adjusted Ventilatory Assist (NAVA) Technology (diaphragm monitor and NAVA mode) vs conventional invasive mechanical ventilation (IMV) for patients at risk of difficult or prolonged weaning from IMV: The UK NAVA Trial
Short title/acronym	UK NAVA
Clinical phase	Phase 3 effectiveness & cost-effectiveness
Purpose of research	To investigate, using a multi-centre, parallel group, pragmatic, randomised controlled trial design, the clinical and cost effectiveness of Neurally Adjusted Ventilatory Assist (NAVA) compared to conventional IMV in adult patients with risk factors for difficult or prolonged weaning from IMV treatment
Trial design	Parallel group randomised controlled trial with internal pilot and cost effectiveness analysis
Participants	Adult ICU patients who are at risk of difficult or prolonged weaning from IMV
Planned sample size	900
Treatment duration	≤28 days
Follow-up duration	6 months following randomisation
Planned trial period	May 1 st 2024 to 31 st September 2028
Inclusion criteria	
 1. Age 18 years or over 2. Receiving invasive mechanical ventilation 3. Expected to stay on IMV for ≥48hrs 4. Any clinical risk factor for difficult or prolonged weaning from IMV
Intervention	NAVA technology uses a specialised nasogastric/orogastric tube (NAVA catheter) to obtain the electrical activity of the diaphragm (EDi) muscle, which is a reliable index of the patient's respiratory drive. Once the NAVA catheter is placed, the EDi is always visible to clinicians, allowing optimisation of ventilator settings in any mode. When the NAVA mode is active, the ventilator triggers, cycles and adjusts support in synchrony and proportion to the EDi.
Control	Conventional invasive ventilator modes (no NAVA Technology)
Primary outcome	Duration of mechanical ventilation (time from randomisation to first successful unassisted breathing or death)
Secondary outcomes	
 1. All-cause mortality at hospital discharge, 2 months and 6 months after randomisation 2. Time to first extubation

	
 3. Reintubation 4. Use of non-invasive ventilation following extubation 5. ICU and hospital length of stay 6. Serious adverse events up to hospital discharge 7. Health related quality of life (EQ-5D-5L) at 2 months and 6 months after randomisation 8. Acute health care use at 6 months following randomisation 
We will conduct a within-trial cost-utility analysis from an NHS hospital care perspective

Statistical methods	
 1. Primary analysis will be intention-to-treat. 2. Primary analysis: Cox proportional hazard regression model will be used to estimate the treatment effect reporting hazards ratio and its 95% confidence interval (CI), using both unadjusted and adjusted analysis. 3. Secondary analysis: Random effects models will be used depending on distribution of the outcomes. The unadjusted and adjusted treatment effects and its 95% CI will be reported.

DRAFT

Abbreviations / glossary

Table 2. Abbreviations / glossary

ARDS	Acute Respiratory Distress Syndrome
CI	Confidence Intervals
COPD	Chronic Obstructive Pulmonary Disease
CoReCCT	Confederation of Respiratory Critical Care Trials
eCRF	Electronic Case Report Form
EDi	Electrical diaphragmatic activity measured in microvolts
ETT	Endotracheal tube
DMC	Data Monitoring Committee
HRQoL	Health-related Quality of Life
ICU	Intensive Care Unit
IMV	Invasive Mechanical Ventilation
ISRCTN	International Standard Registered Clinical/soCial sTudy Number
NAVA	Neurally Adjusted Ventilatory Assist
NAVA Technology	Diaphragm monitoring plus the NAVA ventilation mode
NIV	Non-invasive ventilation
PEEP	Positive-end expiratory pressure
PPI	Public and Patient Involvement
PSV	Pressure Support Ventilation
QALY	Quality Adjusted Life Year
RCT	Randomised Controlled Trial
RASS	Richmond Agitation Sedation Scale
R&D	Research and Development
REC	Research Ethics Committee
SAE	Serious Adverse Event
TMG	Trial Management Group
TSC	Trial Steering Committee
Vt	Tidal Volume

2 BACKGROUND

2.1 EPIDEMIOLOGY AND BURDEN OF THE CONDITION

Invasive mechanical ventilation (IMV) is associated with serious complications and costs, often directly relating to IMV duration [1]. In addition to prolonged physical discomfort and psychological distress, extended durations of IMV treatment increase the risk of infection, lung and muscle damage, and death [2]. About one-third of patients experience difficulties when reducing support (weaning), causing a prolonged duration of IMV [1]. For these reasons, optimised and efficient processes are critical [3].

Across the UK and internationally, the main method of weaning IMV involves use of Pressure Support Ventilation (PSV). Using PSV, the pressure delivered to the lungs during spontaneous breathing efforts is fixed and determined by clinicians based on clinical examination. An important limitation, however, is that the pressure and timing of breaths may not match patient need, which varies over time [4]. Moreover, due to the expertise and time required to set and manually adjust PSV, human factors such as limited staff and expertise can cause errors and delays [5]. These limitations may result in worse patient outcomes including difficult or prolonged IMV [4, 5].

In contrast, automated weaning technologies, such as NAVA, adapt the ventilator automatically according to continuously measured physiological parameters [5, 6]. Using NAVA technology, the electrical activity of the diaphragm (EDi) muscle is continuously measured using a special NAVA catheter. This activity can be used as a monitor of patient respiratory drive, allowing optimisation of ventilator settings in any mode. When the NAVA mode is active, the EDi signal triggers, cycles and adjusts ventilator support within each breath in proportion to diaphragm muscle activity [6].

2.2 EXISTING KNOWLEDGE

Many clinical studies confirm that the NAVA mode improves the synchrony between the ventilator support and the patient's breathing activity [7]. In the NAVA mode, the reduction in diaphragm electrical activity caused by increasing inspiratory assist (and vice versa) causes tidal volume to remain relatively stable over a wide range of ventilator assist. This physiological regulation and pulmonary reflex mechanisms prevent high tidal volumes and facilitate lung-protective ventilation [4]. The same mechanism prevents diaphragm inactivity due to over-assistance, as low diaphragm activity will immediately reduce inspiratory assist [8].

In relation to the effect of NAVA on mechanical ventilation duration (our primary outcome), systematic reviews by Wu (2022, 6 studies, 650 patients), Kampolis (2022, 4 studies, 327 patients) and Yuan (2021, 6 studies, 673 patients) found mean differences of -2.64 days (95% confidence interval (CI), -4.88 to -0.41; $p = 0.02$), -4.89 days (95% CI -10.80 to 1.02; $p = 0.10$), and -2.63 days (95% CI -4.22 to -1.03; $p = 0.001$) respectively [9-11]. Larger reductions were seen in patients with risk factors for longer IMV duration [9], supporting our choice of effect size and inclusion criteria. Although these three meta-analyses suggest benefit in mechanical ventilation and other clinical outcomes, however, they also found low evidence certainty and inconsistency in trials.

2.3 PILOT FEASIBILITY TRIAL AND SURVEYS

To test the feasibility of our trial protocol, we conducted a randomised pilot feasibility trial ($n=78$) [12], a detailed staff survey ($n=301$) [13] and a national clinician survey (unpublished).

Pilot trial results summary

The NAVA mode was initiated successfully in 31/34 (91%) intervention arm patients with median adherence (proportion of eligible weaning time spent in the NAVA mode) of 83.1% (64.0 to 97.1%). Diaphragm monitoring was active in all but one intervention arm patient. In secondary outcomes, the trial found more days free of ventilation at day 28 (median difference (MD) 3.0 days, 95% CI 0.0–11.0; $p = 0.04$), fewer in-hospital deaths (relative risk 0.5, 95% CI 0.2–0.9; $p = 0.032$) and a non-significant difference in mechanical ventilation duration (MD 3.0 days, 95% CI 0.4 to 8.6; $p = 0.13$).

Staff survey results summary

The survey was conducted shortly before the end of recruitment to the pilot trial, and explored attitudes, beliefs and barriers to NAVA Technology use and research. Of the 466 questionnaires distributed, 301 (64.6%) were returned including responses from 236 nurses (78.4%), 53 doctors (17.6%) and 12 physiotherapists (4.0%). In summary the survey found broad support for NAVA use, belief in safety and clinically efficacy, and support and equipoise for research. It also found a perception complexity compared with PSV, low confidence among users and a need for improved training. These findings have informed training materials, study documents and practical measures to improve the intervention and methods of our proposed study.

National survey results summary

The national survey was conducted to understand the availability and use of NAVA and other automated ventilation technologies nationally, receiving responses from 163 ICU clinicians from 86 NHS hospitals (2021 unpublished data). In summary, one or more automated technologies were available at 63/86 (73.3%) responding hospitals and NAVA capable ventilators were available in 28/70 (40%) hospitals. Amongst clinicians working in hospitals with NAVA capable (Getinge) ventilators, 35/62 (56.5%) indicated experience with NAVA. Out of 130 clinicians who completed all survey questions, 81 (62.3%) would use NAVA if available and 41 (31.5%) were unsure; 111 (85.4%) agreed current evidence is uncertain; and 119 (91.5%) wanted more evidence. In relation to our proposed trial, 86 (66.2%) would definitely or probably recruit, 38 (29.2%) would possibly recruit or were unsure, and only 6 (4.6%) said that they would not recruit.

2.4 RESEARCH QUESTION

What is the clinical and cost-effectiveness of NAVA technology compared to conventional IMV, for patients at risk of difficult or prolonged weaning from invasive mechanical ventilation, as defined by the presence of a condition known to be associated with difficult or prolonged IMV weaning?

2.5 NEED FOR A TRIAL

The identification of effective treatments to shorten IMV treatment duration is a priority at this time due to escalating ICU bed pressures and diminishing staffing resources. Prior to the pandemic, up to 60% of UK ICUs did not meet locally agreed staffing numbers and 40% of ICUs closed beds at least once a week due to staff shortages, specifically nursing [14]. Automated technologies may mitigate the risks of sub-optimal weaning care due to continuing workforce issues. Despite the availability and use of NAVA in the NHS, knowledge and understanding of best practice to ensure optimal clinical effectiveness is lacking.

Due to the physiological, clinical and feasibility evidence described above, there have been calls for definitive clinical trials [5, 9] to address the uncertainty around clinical and cost-effectiveness of NAVA. The UK NAVA trial aims to address this knowledge gap with an adequately powered and rigorously trial

comparing NAVA technology to usual care. The trial also addresses a priority of the James Lind Alliance ICU priority setting partnership, 'What is the best way of preventing lung damage of patients receiving respiratory support?' [15].

2.6 CONFEDERATION OF RESPIRATORY CRITICAL CARE TRIALS

UK NAVA sits as one of four trial domains within the Confederation of Respiratory Critical Care Trials (CoReCCT). The confederation was established as a novel concept to group respiratory critical care trials with an overarching aim to streamline trial delivery across areas such as governance, contracting, and data collection. The overriding objective is to improve deliverability by minimising burden on participating sites and participants.

3 TRIAL DESIGN

3.1 TRIAL SUMMARY AND FLOW DIAGRAM

We will conduct a multi-centre, randomised, allocation concealed, controlled, open label, pragmatic, parallel group clinical and cost effectiveness trial with an internal pilot. The internal pilot will run for 6 months in 10 sites (with staggered starts to facilitate site initiation visits and site support). The internal pilot will use identical processes as the main trial and will assess site set-up, screening, participant recruitment, protocol adherence, and cross over rates. Progression criteria are outlined below. All participants included in the internal pilot will be included in the final analyses. The trial will be reported in line with the CONSORT (*Consolidated Standards of Reporting Trials*) statement.³⁸

Once the pilot has been completed sites will be opened as soon as possible in a phased manner ideally over a 10-month period. It is expected around 30 more sites will be opened and recruitment is anticipated to continue for a total of 37 months.

PICO summary

[figure not shown]
Population: Critically ill adults receiving IMV and at risk of difficult or prolonged weaning

Intervention: NAVA Technology (NAVA monitoring and NAVA mode)

Comparator: Conventional invasive ventilator modes (no NAVA Technology)

Outcome: Duration of invasive mechanical ventilation from randomisation (primary clinical effectiveness), plus cost-utility at 6-months

Figure 1. Trial flow diagram

3.2 TRIAL SETTING

The UK NAVA trial will be conducted in approximately 40 ICUs across the UK. These will include university teaching hospitals and district general hospitals in both urban and rural settings. The ICUs must provide evidence that they have access to the trial population, that all consultants in the ICU have clinical equipoise for NAVA technology and agree to maintain trial allocation in patients randomised by their colleagues.

Staff must also demonstrate and document a willingness to comply with the protocol, standard operating procedures, the principles of Good Clinical Practice (GCP) and regulatory requirements and be prepared to participate in training. All new sites will be provided with education and mentoring on NAVA Technology during trial conduct from the research team.

3.3 INTERNAL PILOT

Our trial will include an internal pilot that will run for 6 months (months 6 to 12) with all participants recruited in the pilot included in final analyses. The pilot will take place in 10 representative sites with a staggered start and will recruit 40 patients. The internal pilot will establish our ability to recruit to target, protocol fidelity, crossover rates, and data collection completeness.

During the internal pilot, we will audit screening logs, recruitment rates, reasons for exclusion, protocol fidelity, and crossover rates. We will measure dataset completeness, including completeness of the primary outcome, which we anticipate should be >95% as this is routinely documented in the medical record of all ventilated patients.

We will use a traffic light system to guide progression as recommended in best practice guidelines.[16]

- Green - progress to main trial with review of screening logs and protocol and any barriers to recruitment addressed
- Amber - progress to main trial with ongoing site set-up, review of screening logs and protocol deviations, and protocol review where necessary
- Red - decision to progress to main trial made by the Trial Steering Committee (TSC) and the Health Technology Assessment (HTA) secretariat.

The Data Monitoring Committee (DMC), TSC, and HTA secretariat will review internal pilot data and make recommendations in terms of trial progression.

Total number of participants recruited is based on the recruitment rate and number of sites open during the pilot period. Where the internal pilot is successful with milestones achieved and subsequent trial progression, patients in the pilot will be included in the main analysis. Thresholds are based on a traffic light system [18]: Green (100%), Amber (50%-100%) and Red (<50%).

Table 3. Internal pilot outcomes

	Red	Amber	Green
Recruitment rate/site/month	<0.35	0.35-0.7	0.7
Number of sites opened	<5	5-9	10
Intervention training delivery (percent of open sites)	<50%	50%-100%	100%

Total number of participants recruited	<21	21-42	42
Cross-over (% of recruited)	>5	1-5	0

Total number of participants recruited is based on recruitment rate and number of sites open during the pilot period. Where the internal pilot is successful with milestones achieved and subsequent trial progression, patients in the pilot will be included in the main analysis. Thresholds are based on a traffic light system [18]: Green (100%), Amber (50%-100%) and Red (<50%).

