12.6 TRIAL TIMETABLE AND MILESTONES

The total planned project duration is 52 months. A summary of key trial milestones is shown below.

Table 5: Project Milestones

	Month	Recruitment
Set-up	1-7	N/A
Internal Pilot	8-15	78
Recruitment	16-39	710
Follow up	40-45	N/A
Analysis, reporting & dissemination	46-52	N/A

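### The internal pilot has conflicting windows and recruitment targets, and with a 6-month window the Green and Red totals make no allowance for the staggered site start

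*Protocol*

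**What the plan says.** Three places in the Protocol describe the internal pilot.

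- **Section 3.1:** "The internal pilot will run for 6 months in 10 sites (with staggered starts to facilitate site initiation visits and site support".
- **Section 3.3, text:** "Our trial will include an internal pilot that will run for 6 months (months 6 to 12"), and "The pilot will take place in 10 representative sites with a staggered start and will recruit 40 patients".
- **Section 3.3, Table 3** (Red, Amber, Green in that order): "Recruitment rate/site/month <0.35 0.35-0.7 0.7"; "Number of sites opened <5 5-9 10"; "Total number of participants recruited <21 21-42 42". The notes to the table say that the total rests on the recruitment rate and the number of open sites, and that Green is 100%, Amber 50%-100% and Red below 50%.
- **Section 12.6, Table 5:** "Internal Pilot 8-15 78", that is, months 8 to 15 and 78 recruits.

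Section 3.3 also sets out what the colours do. Green and Amber both lead on to the main trial, Amber with more review. Red passes the decision to the TSC and the HTA secretariat.

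**The concern.** The same pilot has two windows and three recruitment figures. The committees that rate it cannot tell which figure is the plan. The thresholds for total recruited are also fixed numbers, and they look like the product of rate, sites and months with no deduction for sites that open late, although sections 3.1 and 3.3 both say that starts are staggered.

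If so, the rating can mislead in both directions. A pilot that does what was asked on rate and on sites opened can fall short of Green on total recruited. A pilot that reaches Green on total recruited can still be well below the figure in the milestones table.

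**Working it through.** **Inputs from the Protocol.** Ten sites; 6 months (3.1, 3.3) or months 8-15, which is 8 calendar months (12.6); Green rate 0.7 and Red limit 0.35 per site per month (Table 3); totals of 40 (3.3 text), 42 and 21 (Table 3) and 78 (Table 5).

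**Step 1: reproduce Table 3.**
- Green: 0.7 x 10 x 6 = 42.
- Red limit: 0.35 x 10 x 6 = 21.

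Both match exactly. Both use 10 x 6 = 60 site-months, so every site is open for the whole 6 months.

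**Step 2: compare the three totals.**
- 40 lies in Table 3's Amber band (21-42), so a pilot that meets the target in the 3.3 text exactly is not Green.
- 78 cannot be derived from Table 3's inputs. Even over 8 months with no stagger, 0.7 x 10 x 8 = 56. Reaching 78 would need 78 / 80 = 0.975 per site per month.
- 42 / 78 = 54%. This sets a 6-month threshold against an 8-month milestone. Pro-rating 78 linearly to 6 months gives 78 x 6/8 = 58.5, and 42 / 58.5 = 72%. On either basis the pilot is below 100% of the Table 5 figure while Table 3 rates it Green.

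**Step 3: allow for the stagger in a 6-month pilot.** The Protocol gives no opening schedule, so this is an assumption: the first site opens at month 0, the tenth at month R, and the others evenly between. Then

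site-months = 10 x (6 - R/2), and expected recruits = 0.7 x site-months.

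The count is taken as Poisson with that mean, and exactly 42 is counted as Green.

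| R (months) | Site-months | Expected recruits | P(at least 42) | P(below 21) | Rate needed for 42 |
|---|---|---|---|---|---|
| 0 (no stagger) | 60 | 42.0 | 52% | about 0% | 0.70 |
| 1 | 55 | 38.5 | 31% | 0.1% | 0.76 |
| 2 | 50 | 35.0 | 14% | 0.4% | 0.84 |
| 3 | 45 | 31.5 | 4% | 2% | 0.93 |
| 4 | 40 | 28.0 | 0.8% | 7% | 1.05 |
| 5 | 35 | 24.5 | 0.1% | 21% | 1.20 |

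In every staggered row Amber is the most likely colour, although rate and sites are both on target. For example, at R = 2 the Amber probability is 100% - 14% - 0.4%, about 86%; at R = 5 it is 100% - 0.1% - 21%, about 79%.

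**Step 4: repeat with the 8-month window.** Site-months = 10 x (8 - R/2). At R = 4 this is 60, with 42 expected. Over 8 months, 42 is therefore compatible with a stagger of about 4 months.

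**Step 5: band edges.** Exactly 0.7 and exactly 42 each stand in both the Amber and the Green column.

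**The case against.** The strongest reply is that little depends on the colour. Section 3.3 uses the traffic lights to guide progression. Amber proceeds, and Red refers the decision upward. Table 3 shows rate and sites opened on separate rows, so the DMC, TSC and HTA secretariat could see that a low total came from late openings. This stands. A reader might infer that the thresholds would wrongly stop the trial, but the Protocol contains no automatic stop.

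Four further limits also stand.

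- **Risk of Red.** A reader might infer that an on-target pilot has a large chance of Red. That is so only with a slow stagger: about 21% at 5 months, but 0.4% at 2 months. The Protocol does not say which applies.
- **Dependence on the window.** A reader might infer that 42 ignores the stagger in all circumstances. Step 4 shows otherwise for 8 months. But sections 3.1 and 3.3 both say 6 months, and adopting 8 months would still leave 78 unexplained.
- **The 54%.** Read alone, it overstates the gap because the two windows differ; 72% is the like-for-like figure under linear pro-rating.
- **Small differences.** 40 against 42 is 5% and may be rounding. The shared band edges are a drafting matter, since a target met in full is naturally read as Green.

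A reader might also infer that the target rate should be reset to one that delivers the full 900. Nothing worked out here supports that.

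The reply does not remove the conflict over window and target. Nor can the matter be left to a statistical analysis plan, because the Protocol itself fixes these thresholds.

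**Conclusion.** The point holds. That the windows and targets conflict needs no assumption: 6 months (months 6 to 12) against months 8-15, and 40, 42 and 78 recruits, with 78 beyond the 56 that Table 3's rate and sites could give in 8 months.

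The stagger point is conditional on the 6-month window. Given that window, Green and Red for total recruited assume 60 site-months, and any stagger makes Amber the most likely result for a pilot on target for rate and sites. How far short it falls depends on the assumed even opening and on Poisson counts. Differences in rate between sites would widen the spread, so the tail probabilities are indicative.

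The consequence is a misleading colour and an unclear benchmark for the bodies that advise on progression. The document gives no ground for expecting a wrongful stop. Because pilot participants enter the final analysis, the estimate of the treatment effect is not touched. The thresholds should be corrected before the pilot is rated.

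**What to change.** 1. State one pilot window and one recruitment target, and use them in sections 3.1 and 3.3, Table 3 and Table 5.
2. Write down the planned opening schedule for the ten sites. Set Green for total recruited at the target rate x the planned open site-months. Set Amber at 50% to below 100% of that number, and Red below 50%. As an illustration only, 6 months with an even 3-month opening gives 45 site-months and 0.7 x 45 = 31.5, so Green would be 32 or more and Red 15 or fewer (below 15.75).
3. As a tidy-up, make the bands exclusive: Green at or above the threshold, Amber below it.

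The cost is edits to two tables and a few sentences, agreed with the TSC and the funder. Participants are not affected.
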